## Project Abstract

Infertility affects 12% of couples in the United States. In vitro fertilization (IVF) is the most advanced treatment for infertility. Despite decades of improvements in hormonal drug therapy and laboratory techniques, IVF embryos continue to have low implantation potential (~30%/embryo). Therefore, it is not uncommon to transfer multiple embryos to the uterus in order to enhance success. As a result, approximately 30% of IVF pregnancies result in multiple gestation, which lead to higher morbidity and mortality of the mothers and infants. The best method to reduce multiple birth and associated morbidity and mortality is to transfer a single embryo with enhanced implantation potential. A recent meta-analysis of acupuncture for IVF showed it may augment IVF success by ~10%, although the underlying mechanism remains unclear. We hypothesize that acupuncture enhances IVF success by enhancing the perfusion of pelvic organs including the ovaries and the uterus. Since undergoing IVF treatment is a stressful process to most patients, we further hypothesize that acupuncture stabilizes the mind-body interaction by optimizing the psychological well-being of patients receiving IVF treatment.

Experimental Approach: (1) Participants: Women (ages 21 to 42) who seek IVF treatment at the Center for Fertility & Reproductive Surgery will be eligible for the study. Seventy women will be recruited and randomly assigned to either the intervention (acupuncture plus standard care) or the comparison (standard care alone) group. (2) Intervention: Participants in the intervention group will receive 3 acupuncture sessions during the project with the first treatment between day 6–8 of the stimulated IVF cycle, second treatment on the day of embryo transfer and the third treatment post-transfer, within 48 hours. Participants in the comparison group will receive no intervention but will receive standard care. (3) Measures: The primary outcome measures include prostacyclin and thromboxane vasoactive biomarkers. Secondary outcome measures include perceived stress levels. (4) Procedure: Upon IRB approval, an informed consent will be provided to all participants. Pre- and post- acupuncture urinary metabolites of prostacyclin and thromboxane will be assessed. A standardized Perceived Stress Scale will be administered before each acupuncture session for the study group, and before a 30-40-minute waiting period for the control group.

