### ***Research Design and Methods***

This is a prospective, randomized, controlled study. Participants will be women in the Principal Investigator's practice seeking IVF. Participants will be randomized 1:1 into either the acupuncture group or the standard of care (no acupuncture) group. Each group will have 3 study visits during their 8-week IVF cycle.

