#### ***Power analysis***

With 35 patients allocated to each group, assuming the Student's T-test will be used to determine the differences between two independent samples, effect sizes  $d \geq 0.6$  will be found statistically significant with alpha .05 and power .80. In practical terms, since the PSS validation samples showed a mean about 13.5 with variance=6.2, only averaged differences greater than 1.5 raw score points in PSS will be found statistically significant.

We plan to seek extramural funding in the future. We will use the data obtained from this pilot study to perform power analysis and to calculate the number of participants needed in future proposals.

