**Norm Table for the PSS 10 item inventory**

Category	N	Mean	S.D.
Gender			
Male	926	12.1	5.9
Female	1406	13.7	6.6
Age			
18-29	645	14.2	6.2
30-44	750	13.0	6.2
45-54	285	12.6	6.1
55-64	282	11.9	6.9
65 & older	296	12.0	6.3
Race			
white	1924	12.8	6.2
Hispanic	98	14.0	6.9
black	176	14.7	7.2
other minority	50	14.1	5.0

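### The power statement uses the PSS standard deviation (6.2) as a variance, so its detectable difference of 1.5 points should be about 3.7 points or more

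*Combined protocol and SAP*

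**What the plan says.** The Power analysis section (under Research Design and Methods) sets out the calculation in two steps. The first is standardised: "With 35 patients allocated to each group", and "assuming the Student's T-test will be used to determine the differences between two independent samples", the study is said to detect d of 0.6 or more at alpha 0.05 with 80% power. It does not say whether alpha is one- or two-sided. The second step turns d into PSS points: "PSS validation samples showed a mean about 13.5 with variance=6.2, only averaged differences greater than 1.5 raw score points" are said to reach significance.

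The Addendum reproduces the norm table for the 10-item PSS, with columns "Category N Mean S.D". Two rows matter most here: "30-44 750 13.0 6.2" and "Female 1406 13.7 6.6". The 18-29 row has mean 14.2 and the same last-column value, 6.2.

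The Project Abstract places PSS below the urinary biomarkers: "Secondary outcome measures include perceived stress levels".

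**The concern.** The power paragraph calls 6.2 a variance, while the norm table in the same document shows 6.2 as a standard deviation. If the label alone were wrong, this would be a typing slip. The 1.5-point figure, however, depends on the square root of 6.2, so the error has reached the result.

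This is the only place where the plan says, in raw units of any outcome, what the trial can detect. Stress is the subject of the second specific aim. A reader who trusts the 1.5 would take a null PSS result as good evidence against effects of 1.5 to 3.7 points, when the trial has little power for most of that range.

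**Working it through.** **Inputs**
- 35 per group, independent-samples t-test, d = 0.6, alpha 0.05, power 0.80 (Power analysis). Allocation is 1:1 (Research Design and Methods).
- PSS spread of 6.2, called a variance (Power analysis).
- Norm-table SDs (Addendum): 6.2 for ages 18-29, 6.2 for ages 30-44, 6.6 for women, and 5.0 as the smallest in the table.
- Eligible age 21-42, women only (Inclusion criteria).

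**1. Reproduce the plan's figure.** Raw difference = d × SD. With 6.2 as a variance, SD = √6.2 = 2.490 and 0.6 × 2.490 = 1.494, which rounds to the stated 1.5.

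**2. Is 6.2 a variance or an SD?** The table gives 6.2 only as an SD. The two age bands covering the eligible women both have SD 6.2, and their N-weighted mean is (645 × 14.2 + 750 × 13.0)/1395 = 13.55, in line with the plan's mean of about 13.5. The smallest SD in the table, 5.0, is a variance of 25. No listed group has a variance near 6.2.

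**3. Correct the conversion, keeping d = 0.6.**
- SD 6.2: 0.6 × 6.2 = 3.72 points. Ratio to the plan's figure: 3.72/1.494 = 2.49.
- SD 6.6 (women): 0.6 × 6.6 = 3.96 points. Ratio: 3.96/1.494 = 2.65.
- SD 5.0 (smallest listed): 0.6 × 5.0 = 3.00 points, still twice the stated 1.5.

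**4. Check d = 0.6 itself** (noncentral t, 35 per group, 68 degrees of freedom).

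| Test at 5% | Power at d = 0.6 | d for 80% power | Points, SD 6.2 | Points, SD 6.6 |
|---|---|---|---|---|
| One-sided | 0.800 | 0.600 | 3.72 | 3.96 |
| Two-sided | 0.697 | 0.679 | 4.21 | 4.48 |

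The plan's d = 0.6 therefore holds at 80% power only for a one-sided test.

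**5. Power for a true difference of 1.5 points.**
- SD 6.2: d = 1.5/6.2 = 0.242, giving power 0.170 two-sided and 0.260 one-sided.
- SD 6.6: d = 1.5/6.6 = 0.227, giving power 0.155 two-sided and 0.241 one-sided.
- For scale, 80% two-sided power for 1.5 points at SD 6.2 would need about 269 per group (normal approximation).

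**6. Could 1.5 be a significance cut-off instead of a powered difference?** The smallest significant observed difference is t × SD × √(2/35). With SD 6.2 this is 2.96 points two-sided and 2.47 points one-sided. With SD 5.0 it is 2.39 and 1.99. None is as low as 1.5.

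**7. Could a baseline-adjusted or change-score analysis give 1.5?** It would need a residual or change SD of 1.5/0.6 = 2.5. From SD 6.2 that requires a correlation of 1 − (2.5/6.2)²/2 = 0.919 for change scores, or √(1 − (2.5/6.2)²) = 0.915 for covariate adjustment. The documents give no such correlation, and the section assumes a comparison of two independent samples.

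**The case against.** The strongest reply concerns weight. The sample size of 70 rests on d = 0.6 and does not use 6.2. PSS is secondary, the study is a pilot, and no decision rule depends on 1.5 points. The section also says that later sample sizes will be worked out from this study's own data, so the 1.5 need not carry forward. All of this stands, and it is why the point is a correction to a stated sensitivity and does not challenge the design.

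A second reply is that the Power analysis section refers to validation samples without citing the norm table, and no row there has a mean of exactly 13.5. The link is indeed inferred. It is a strong inference, because the SD matches both relevant age bands and their pooled mean is 13.55. The conclusion does not need an exact row either: every SD in the table gives at least 3.0 points at d = 0.6.

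A third reply is that 3.7 points is conditional, since it is the 80%-power difference only for a one-sided test and for SD 6.2. That is correct, but a two-sided test or the female SD makes the understatement larger.

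**Conclusion.** The statement is wrong as written. On the plan's own d = 0.6, the PSS difference is 3.7 points (SD 6.2) to 4.0 points (SD 6.6), about 2.5 times the stated 1.5 or slightly more. If the test is two-sided, the difference detectable with 80% power is 4.2 to 4.5 points. No reading of the sentence that the documents support gives 1.5.

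These figures assume that the norm-table SDs apply to women having IVF, that the comparison is the stated independent-samples t-test, and that all 35 per group supply PSS data. Participation ends if transfer is cancelled, and the calculation makes no allowance for this, so the real detectable difference may be larger. The point should be corrected. It does not affect enrolment or the primary outcomes.

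**What to change.** Rewrite the power paragraph so that the spread, d, sidedness and raw points agree:
- Give 6.2 as an SD, cite the norm table, and add the female value of 6.6.
- State whether the test is one- or two-sided. Either (a) keep d = 0.6 with a one-sided 5% test and state 3.7 points (SD 6.2) to 4.0 points (SD 6.6), or (b) use a two-sided 5% test, change d to 0.68 and state 4.2 to 4.5 points. This is a design choice for the investigators. The documents give no reason for a one-sided test, so option (a) would need one.
- Describe the result as the difference detectable with 80% power, not as the smallest difference that can be significant.
- Add that a null PSS result cannot rule out smaller differences.

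The cost is one paragraph of text and, because this is an IRB-approved version, possibly an IRB submission. Enrolment, visits and data collection do not change. The stated sensitivity becomes less favourable.

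### The power analysis presents the effect detectable with 80% power as the smallest observed PSS difference that can be significant; with 35 per arm these are different figures.

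*Combined protocol and SAP*

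**What the plan says.** The Power analysis section of the combined protocol and SAP starts from the planned size, "With 35 patients allocated to each group", and names the test: "assuming the Student's T-test will be used to determine the differences between two independent samples". Effects of d = 0.6 or more, it continues, "will be found statistically significant with alpha .05 and power .80". Whether alpha is one-sided or two-sided is not stated.

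The section then converts this to Perceived Stress Scale (PSS) points. The spread it uses is given as "since the PSS validation samples showed a mean about 13.5 with variance=6.2", and the conclusion drawn is that "only averaged differences greater than 1.5 raw score points in PSS will be found statistically significant".

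The PSS addendum contains a table headed "Norm Table for the PSS 10 item inventory". Its last column is headed S.D. and shows 6.2 for ages 18-29 and for ages 30-44, and 6.6 for women.

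**The concern.** Two quantities have been merged. One is a true difference that a trial of this size would detect with a given probability. The other is the observed difference at which the t-test reaches p < 0.05. At 80% power the second is always smaller than the first, because a trial whose true effect sat exactly at the cut-off would have only about 50% power.

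The word "only" in the raw-score sentence turns the power figure into an exclusion: nothing smaller is to be significant. That gives the reader a wrong figure for what the t-test will do. The confusion would survive correction of the spread and of the sidedness, since it lies in the conversion and not in the inputs. The section also says that the pilot data will feed later sample-size calculations, so the distinction between a detectable effect and an observed cut-off should be right here.

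**Working it through.** **Inputs.** 35 per arm, two-sample Student's t-test, alpha .05, power .80, d = 0.6 and variance 6.2 (Power analysis); 1:1 allocation (Research Design and Methods); S.D. 6.2 and 6.6 (PSS norm table). Degrees of freedom: 2 × 35 − 2 = 68. The power section makes no allowance for dropout, so 35 per arm is used as stated. Sidedness is not stated, so both cases are shown.

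**1. Reproducing the plan's figures.** Power comes from the noncentral t distribution with noncentrality 0.6 × √(35/2) = 2.51.
- One-sided alpha .05: power at d = 0.6 is 0.800, and the 80%-power effect is d = 0.600. The plan's figure reproduces.
- Two-sided alpha .05: power at d = 0.6 is 0.697, and the 80%-power effect is d = 0.679. The plan's figure does not reproduce.
- Raw scale: 0.6 × √6.2 = 0.6 × 2.49 = 1.49, which rounds to the stated 1.5.

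So the 1.5 is the one-sided 80%-power effect, with 6.2 read as a variance.

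**2. Smallest observed difference reaching p < 0.05.** In SD units this is t_crit × √(2/35), with √(2/35) = 0.2390.
- Two-sided: 1.9955 × 0.2390 = 0.477
- One-sided: 1.6676 × 0.2390 = 0.399

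The 0.6 SD rule exceeds these by 26% (0.6/0.477 = 1.26) and 51% (0.6/0.399 = 1.51).

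**3. In PSS points.** Cut-off = SD units × SD; 80%-power difference = 0.679 × SD (two-sided) or 0.600 × SD (one-sided).

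| SD used | Cut-off, two-sided | Cut-off, one-sided | 80% power, two-sided | 80% power, one-sided |
|---|---|---|---|---|
| 2.49 (variance 6.2, as stated) | 1.19 | 0.99 | 1.69 | 1.49 |
| 6.2 (norm table, ages 18-44) | 2.96 | 2.47 | 4.21 | 3.72 |
| 6.6 (norm table, female) | 3.15 | 2.63 | 4.48 | 3.96 |

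**4. What an observed 1.5 points would give.**
- SD 2.49: t = 1.5 / (2.49 × 0.2390) = 2.52, two-sided p = 0.014. This is well inside the significant region, so 1.5 is too high as a cut-off.
- SD 6.2: t = 1.5 / (6.2 × 0.2390) = 1.01, two-sided p = 0.32, one-sided p = 0.16. This is not significant, so 1.5 is too low, by a factor of 2.96/1.5 = 2.0 two-sided or 2.47/1.5 = 1.6 one-sided. Power for a true difference of 1.5 points would be 17% two-sided or 26% one-sided.

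**5. How often the two quantities part company.** If the true d is 0.6 and the test is two-sided, about 19% of trials would give an observed d between 0.477 and 0.6: significant, yet below the stated threshold. About 30% (1 − 0.697) would not be significant at all.

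**The case against.** The first sentence of the power section carries its own qualifier, power .80. It is loose shorthand and does not claim that every true effect of 0.6 will be detected. That stands; the error is in the second sentence.

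A reader might infer that 1.5 points is a decision threshold, so that a significant result could be declared non-significant. The documents do not support this. The sentence offers a practical illustration in a power section, the t-test would decide significance, and nowhere is 1.5 points made a formal rule.

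A reader might also infer that a null result will be taken to rule out d = 0.6. The documents do not say so. It is a possible risk: an observed d of 0.3 is non-significant, yet its approximate two-sided 95% interval, 0.3 ± 0.477, runs from −0.18 to 0.78 and includes 0.6. But that reading is not in the plan.

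Third, it is tempting to say simply that the threshold is too high. In raw points the direction depends on the spread: too high if 6.2 is a variance, too low if it is an SD, as the norm table has it. The spread error is also the larger of the two, a factor of 6.2/2.49 = 2.5.

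Finally, the PSS is a secondary outcome in a pilot, and the section gives no raw threshold for the primary biomarkers. This limits the consequences. It does not make the sentence correct, because the figure is wrong as a cut-off on either spread and either sidedness.

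**Conclusion.** The point holds as a correction to a stated figure. The power section gives the effect detectable with 80% power as the smallest observed difference that will be significant. On the standardised scale the rule is 0.6 SD where the cut-off is 0.48 (two-sided) or 0.40 (one-sided). At the stated variance it is 1.5 points where the cut-off is 1.19 or 0.99. At the norm table's S.D. of 6.2 the error reverses: 1.5 points against 2.96 or 2.47.

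The 80% label on d = 0.6 is itself right only for a one-sided alpha of .05, which the plan does not declare; two-sided power is about 70%.

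These results assume 35 analysed per arm, a common SD and the t-test named in the plan. The raw-point figures also assume that the norm-table spread carries over to women undergoing IVF, which the documents do not show.

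**What to change.** Make three corrections together in the Power analysis section:

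- State whether alpha .05 is one-sided or two-sided.
- Treat 6.2 as a standard deviation, in line with the norm table, and say which row is used (6.2 for ages 18-29 and 30-44, or 6.6 for women).
- Replace the raw-score sentence with two separately labelled figures:
  - *True difference with 80% power.* Two-sided: d = 0.68, about 4.2 PSS points at S.D. 6.2 or 4.5 at 6.6. One-sided: d = 0.60, about 3.7 or 4.0 points.
  - *Smallest observed difference reaching p < 0.05.* Two-sided: 0.48 SD, about 3.0 points at S.D. 6.2 or 3.1 at 6.6. One-sided: 0.40 SD, about 2.5 or 2.6 points.

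Changing 1.5 to 1.19 and nothing else would move the raw figure further from the norm-table value.

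Reporting mean differences with 95% confidence intervals would also guard against misreading a null result. That is good practice and not part of correcting this error.

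The cost is about two rewritten sentences, with no change to the design or the sample size. If two-sided testing is chosen, the section must accept either 80% power at d = 0.68 or about 70% at d = 0.6.

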#### *Assessment of Self-Perceived Stress in Treatment and Control Group*

To determine whether acupuncture contributes to stress reduction, study participants in the treatment group will complete the Perceived Stress Scale (Cohen, 1983 see Addendum) to assess self-perceived stress cycle days 6 through 8 of ovarian stimulation, on the day of embryo transfer, pre-embryo transfer and post-embryo transfer, but before the

pregnancy test, within 48 hours of transfer. Participants in this group will complete this scale before and after their acupuncture treatment.

Study participants in the control group will complete the same Perceived Stress Scale questionnaire once during days 6 through 8 of ovarian stimulation, on the day of embryo transfer, pre-embryo transfer and post-embryo transfer, but prior to the pregnancy test, within 48 hours of transfer.. In the event that the embryo transfer must be postponed for clinical reasons, the post-treatment questionnaire will be performed 3 to 7 days after the oocyte retrieval.

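### The visit-1 stress score, planned in both arms before any session or wait, is not used in the only PSS comparison the plan names, so Aim 2 is less precise than its data allow.

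*Combined protocol and SAP*

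**What the plan says.** The Power analysis section starts from "With 35 patients allocated to each group", "assuming the Student's T-test will be used to determine the differences between two independent samples", and states that effects of d = 0.6 or more "will be found statistically significant with alpha .05 and power .80". It does not say whether the test is one- or two-sided. It then converts d to the PSS: with a mean of about 13.5 and a variance of 6.2, "only averaged differences greater than 1.5 raw score points in PSS will be found statistically significant". No section gives a baseline-adjusted, change-score or repeated-measures analysis of the PSS, or says which visit or visits are compared.

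On data collection, the Project Abstract says that the scale "will be administered before each acupuncture session for the study group, and before a 30-40-minute waiting period for the control group". The section on assessment of self-perceived stress schedules it in both arms on stimulation days 6 to 8, on the day of transfer before transfer, and after transfer. That section adds an after-session form in the acupuncture arm only. Controls "will complete the same Perceived Stress Scale questionnaire once during days 6 through 8 of ovarian stimulation", with no statement that the form precedes the wait.

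**The concern.** Women differ in their general level of stress, and an unadjusted comparison leaves those differences in the error term. A score taken before the first needle or wait removes part of them at no collection cost.

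The visit-1 score is also the only covariate that fits the design. Controls have no after-wait form, so there is no matched before/after pair within a visit. The matched outcomes are the pre-session and pre-wait forms at visits 2 and 3. The visit-1 form comes before treatment, so averaging it into the outcome would dilute any effect.

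What is at stake is the precision of Aim 2, a secondary outcome, and the usefulness of the estimate for the later sample-size calculations that the protocol says this pilot will feed.

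**Working it through.** **Inputs.** From the Power analysis section: 35 per arm, alpha 0.05, d = 0.6. From the norm table in the addendum: S.D. 6.2 (ages 18-29 and 30-44) and 6.6 (women). Assumed: the correlation r between visit 1 and a later visit, 0.3 to 0.7; the correlation q between visits 2 and 3; and 28 to 32 per arm remaining at visits 2 and 3.

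**1. The plan's own figure.** Noncentral t, 68 df, noncentrality d × √(n/2) = 0.6 × √17.5 = 2.51.
- One-sided 0.05: power 0.80, as stated.
- Two-sided 0.05: power 0.70. Power of 80% needs d = 0.68, which is 0.679 × 6.2 = 4.2 points or 0.679 × 6.6 = 4.5 points.

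**2. One later visit adjusted for visit 1.** The residual S.D. is multiplied by √(1 − r²), and one df is lost (67 df at 35 per arm). Two-sided power at d = 0.6:

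| r | √(1 − r²) | 35 per arm | 32 | 30 | 28 |
|---|---|---|---|---|---|
| 0.3 | 0.954 | 0.74 | 0.70 | 0.67 | 0.64 |
| 0.5 | 0.866 | 0.81 | 0.78 | 0.75 | 0.72 |
| 0.7 | 0.714 | 0.93 | 0.91 | 0.89 | 0.87 |

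Power of 80% needs r of about 0.47 with 35 per arm, 0.54 with 32, 0.58 with 30 and 0.62 with 28. Whichever way the test is sided, the confidence interval shortens by about 5%, 13% and 29% at r = 0.3, 0.5 and 0.7 (one minus the factor in the second column).

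**3. Mean of visits 2 and 3, adjusted.** The residual variance, in units of the single-visit variance, is (1 + q)/2 − r². Visit 3 may fall on the same day as visit 2 and is planned within 48 hours of transfer, and the form asks about the last month, so q is probably high. Take r = 0.5 and 35 per arm:
- q = 0.8: 0.90 − 0.25 = 0.65, factor 0.806. Power is 0.87. Detectable difference 0.679 × 0.806 × 6.2 = 3.4 points (3.6 at S.D. 6.6).
- q = 0.9: 0.95 − 0.25 = 0.70, factor 0.837. Power is 0.84. Detectable difference 3.5 points (3.75 at S.D. 6.6).

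Against 0.81 for one adjusted visit, averaging adds little.

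**4. The 1.5 points.** 0.6 × √6.2 = 1.49, so the figure holds only if 6.2 is a variance. With 6.2 as an S.D., d = 0.6 is 3.7 points, and 1.5 points is d = 1.5/6.2 = 0.24. Two-sided power for that is 0.17 unadjusted. With one adjusted visit it is 0.21 at r = 0.5 and 0.29 at r = 0.7; 80% would need r of about 0.93.

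**The case against.** **The t-test is a sizing assumption, not a declared analysis.** This is fair. A reader might infer that the protocol commits to an unadjusted analysis; it only assumes one. But nothing else is specified for Aim 2, so the gap remains.

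**There may be no shortfall.** A reader might infer that the stated 80% is wrong. Sidedness is not given and a one-sided test reproduces it, so the 0.70 applies only to a two-sided test. The precision gain applies to either.

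**Adjustment does not guarantee 80%.** This stands. It depends on an r that the documents do not give, and participation ends if transfer is cancelled (Removal from study), with no allowance for loss. One-month recall supports a fairly high r, but it may also shrink any effect visible at visits 2 and 3.

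**Averaging looks like a large gain.** Setting q = r = 0.5 gives power of 0.94 and 3.0 to 3.2 points. That requires visits possibly hours apart to correlate no better than visits further apart, which the schedule makes implausible. Part of that gain would also come from averaging: the unadjusted mean at q = 0.5 already has a residual variance of 0.75, the same as one adjusted visit at r = 0.5.

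**Visit 1 may not be a clean baseline.** Randomization follows eligibility, and its order relative to the visit-1 form is not stated. Without a sham, women know their arm. Under Poor Response to Egg Retrieval, a woman may also repeat visits 1 to 3 in a later cycle with the same allocation, so a repeated visit-1 form could follow an earlier session. Both points stand and are handled in the fix.

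**Conclusion.** The point holds as a missed gain in precision on a secondary outcome. With 35 per arm, a two-sided 5% test and d = 0.6, power rises from 0.70 to 0.74, 0.81 or 0.93 as r goes from 0.3 to 0.5 to 0.7. At r = 0.5 it is 0.72 to 0.78 if 28 to 32 per arm remain. The adjusted mean of both later visits gives 0.84 to 0.87 at r = 0.5 and q = 0.8 to 0.9 with no loss. All values of r, q and loss are assumptions.

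The documents do not support the stronger reading that adjustment makes the plan's PSS statement true. The recovery concerns d = 0.6, which is 3.7 to 4.0 points at S.D. 6.2 to 6.6, and not 1.5 points. The conflict over whether 6.2 is a variance or an S.D. is a separate error, and adjustment leaves it in place.

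**What to change.** In the Power analysis section, state that Aim 2 compares the arms on the matched pre-session (acupuncture) and pre-wait (control) PSS at visits 2 and 3. Use one repeated-measures linear model with arm, visit, arm-by-visit and the visit-1 pre-session/pre-wait PSS as covariate. State that the test is two-sided, and report the arm difference averaged over visits 2 and 3 with its 95% confidence interval.

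Use visit 1 only as covariate. For women who restart after a poor response, take their first visit-1 form. Where possible, have that form completed before the randomization envelope is opened. Bring the assessment section into line with the Project Abstract on when the control form is completed.

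Report the unadjusted difference as a sensitivity analysis, but do not read the gap between the two results as the size of an expectation effect. By chance alone, the visit-1 arm difference has a standard error of 6.2 × √(2/35) = 1.5 points (1.6 at S.D. 6.6), and the gap mixes the two. Correct the 1.5-point statement separately.

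The cost is one paragraph and one model, with no new data. The downside is that, if visit 1 follows allocation in this open trial, any expectation effect already present is partly adjusted away.
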